10.42 General reporting instructions

The Mayo IND Coordinator will assist the sponsor-investigator in the processing of expedited adverse events and forwarding of suspected unexpected serious adverse reactions (SUSARs) to the FDA and IRB.

Use Mayo Expedited Event Report form

[REDACTED] for investigational agents or commercial/investigational agents on the same arm.

Submit to [REDACTED]

10.43 Reporting of re-occurring SAEs

ALL SERIOUS adverse events that meet the criteria outlined in table 10.41 MUST be immediately reported to the sponsor within the timeframes detailed in the corresponding table. This reporting includes, but is not limited to SAEs that re-occur again after resolution.

10.5 Other Required Reporting

10.51 Unanticipated Problems Involving Risks to Subjects or Others (UPIRTSOS)

Unanticipated Problems Involving Risks to Subjects or Others (UPIRTSOS) in general, include any incident, experience, or outcome that meets **all** of the following criteria:

1. Unexpected (in terms of nature, severity, or frequency) given (a) the research procedures that are described in the protocol-related documents, such as the IRB-approved research protocol and informed consent document; and (b) the characteristics of the subject population being studied;
2. Related or possibly related to participation in the research (in this guidance document, possibly related means there is a reasonable possibility that the incident, experience, or outcome may have been caused by the procedures involved in the research); and
3. Suggests that the research places subjects or others at a greater risk of harm (including physical, psychological, economic, or social harm) than was previously known or recognized.

Some unanticipated problems involve social or economic harm instead of the physical or psychological harm associated with adverse events. In other cases, unanticipated problems place subjects or others at increased *risk* of harm, but no harm occurs.

Note: If there is no language in the protocol indicating that pregnancy is not considered an adverse experience for this trial, and if the consent form does not indicate that subjects should not get pregnant/impregnate others, then any pregnancy in a subject/patient or a male patient's partner (spontaneously reported) which occurs during the study or within 120 days of completing the study should be reported as a UPIRTSO.

Mayo Clinic Cancer Center (MCCC) Institutions:

If the event meets the criteria for IRB submission as a Reportable Event/UPIRTSO, Use Mayo Expedited Event Report form

[REDACTED] and appropriate documentation to [REDACTED] The Mayo Regulatory Affairs Office will review and process the submission to the Mayo Clinic IRB.

10.52 Death

Note: A death on study requires both routine and expedited reporting regardless of causality, unless as noted below. Attribution to treatment or other cause must be provided.

Any death occurring within 30 days of the last dose, regardless of attribution to an agent/intervention under an IND/IDE requires expedited reporting within 24-hours.

Any death occurring greater than 30 days with an attribution of possible, probable, or definite to an agent/intervention under an IND/IDE requires expedited reporting within 24-hours.

Reportable categories of Death

- Death attributable to a CTCAE term.
- Death Neonatal: A disorder characterized by cessation of life during the first 28 days of life.
- Death NOS: A cessation of life that cannot be attributed to a CTCAE term associated with Grade 5.
- Sudden death NOS: A sudden (defined as instant or within one hour of the onset of symptoms) or an unobserved cessation of life that cannot be attributed to a CTCAE term associated with Grade 5.
- Death due to progressive disease should be reported as **Grade 5 “Neoplasms benign, malignant and unspecified (including cysts and polyps) – Other (Progressive Disease)”** under the system organ class (SOC) of the same name. Evidence that the death was a manifestation of underlying disease (e.g., radiological changes suggesting tumor growth or progression; clinical deterioration associated with a disease process) should be submitted.

10.53 Secondary Malignancy

- A **secondary malignancy** is a cancer caused by treatment for a previous malignancy (e.g., treatment with investigational agent/intervention, radiation or chemotherapy). A secondary malignancy is not considered a metastasis of the initial neoplasm.
- All secondary malignancies that occur following treatment with an agent under an IND/IDE will be reported. Three options are available to describe the event:
 - Leukemia secondary to oncology chemotherapy (e.g., Acute Myelocytic Leukemia [AML])
 - Myelodysplastic syndrome (MDS)
 - Treatment-related secondary malignancy

- Any malignancy possibly related to cancer treatment (including AML/MDS) should also be reported via the routine reporting mechanisms outlined in each protocol.

10.54 Second Malignancy

A second malignancy is one unrelated to the treatment of a prior malignancy (and is NOT a metastasis from the initial malignancy). Second malignancies require ONLY routine reporting unless otherwise specified.

10.55 Pregnancy, Fetal Death, and Death Neonatal

If a female subject (or female partner of a male subject) taking investigational product becomes pregnant, the subject taking should notify the Investigator, and the pregnant female should be advised to call her healthcare provider immediately. The patient should have appropriate follow-up as deemed necessary by her physician. If the baby is born with a birth defect or anomaly, a second expedited report is required.

Prior to obtaining private information about a pregnant woman and her infant, the investigator must obtain consent from the pregnant woman and the newborn infant's parent or legal guardian before any data collection can occur. A consent form will need to be submitted to the IRB for these subjects if a pregnancy occurs. If informed consent is not obtained, no information may be collected.

In cases of fetal death, miscarriage or abortion, the mother is the patient. In cases where the child/fetus experiences a serious adverse event other than fetal death, the child/fetus is the patient.

NOTE: When submitting Mayo Expedited Adverse Event Report reports for "Pregnancy", "Pregnancy loss", or "Neonatal loss", the potential risk of exposure of the fetus to the investigational agent(s) or chemotherapy agent(s) should be documented in the "Description of Event" section. Include any available medical documentation. Include this form:

10.551 Pregnancy

Pregnancy should be reported in an expedited manner as **Grade 3 "Pregnancy, puerperium and perinatal conditions - Other (pregnancy)"** under the Pregnancy, puerperium and perinatal conditions SOC. Pregnancy should be followed until the outcome is known.

10.552 Fetal Death

Fetal death is defined in CTCAE as "A disorder characterized by death in utero; failure of the product of conception to show evidence of respiration, heartbeat, or definite movement of a voluntary muscle after expulsion from the uterus, without possibility of resuscitation."

Any fetal death should be reported expeditiously, as **Grade 4 "Pregnancy, puerperium and perinatal conditions - Other (pregnancy loss)"** under the Pregnancy, puerperium and perinatal conditions SOC.

10.553 Death Neonatal

Neonatal death, defined in CTCAE as “A disorder characterized by cessation of life occurring during the first 28 days of life” that is felt by the investigator to be at least possibly due to the investigational agent/intervention, should be reported expeditiously.

A neonatal death should be reported expeditiously as **Grade 4** **“General disorders and administration - Other (neonatal loss)”** under the General disorders and administration SOC.

10.6 Required Routine Reporting

10.61 Baseline and Adverse Events Evaluations

Pretreatment symptoms/conditions to be graded at baseline and adverse events to be graded at each evaluation.

Grading is per CTCAE v4.0 **unless** alternate grading is indicated in the table below:

System Organ Class (SOC)	Adverse event/Symptoms	Baseline	Each evaluation
Blood and lymphatic system disorders	Anemia	X	X
Gastrointestinal disorders	No. of stools	X	
	Diarrhea		X
	Mucositis oral		X
	Nausea	X	X
	Oral dysesthesia		X
	Vomiting		X
	Weight loss		X
General disorders and administration site conditions	Fatigue	X	X
Renal and urinary disorders	Proteinuria	X	X
Respiratory, thoracic and mediastinal disorders	Cough	X	X
Skin and subcutaneous disorders	Rash maculo-papular	X	X
	Palmar-plantar erythrodysesthesia syndrome	X	X
Vascular disorders	Hypertension	X	X

10.62 Submit via appropriate MCCC Case Report Forms (i.e., paper or electronic, as applicable) the following AEs experienced by a patient and not specified in Section 10.6:

10.621 Grade 2 AEs deemed *possibly, probably, or definitely* related to the study treatment or procedure.

10.622 Grade 3 and 4 AEs regardless of attribution to the study treatment or procedure.

10.623 Grade 5 AEs (Deaths)

10.6231 Any death within 30 days of the patient’s last study treatment or procedure regardless of attribution to the study treatment or procedure.

10.6232 Any death more than 30 days after the patient's last study treatment or procedure that is felt to be at least possibly treatment related must also be submitted as a Grade 5 AE, with a CTCAE type and attribution assigned.

10.7 Late Occurring Adverse Events

Refer to the instructions in the Forms Packet (or electronic data entry screens, as applicable) regarding the submission of late occurring AEs following completion of the Active Monitoring Phase (i.e., compliance with Test Schedule in Section 4.0).

10.8 *[Insert industry partner name] Additional Event Reporting Instructions*

Insert any additional language requested by industry partners in this section.

11.0 TREATMENT EVALUATION

NOTE: This study uses protocol RECIST v1.1 template dated 2/16/2011. See the footnote for the table regarding measureable disease in Section 11.44, as it pertains to data collection and analysis.

Response and progression will be evaluated in this study using the new international criteria proposed by the revised Response Evaluation Criteria in Solid Tumors (RECIST) guidelines (version 1.1)(Eisenhauer, Therasse et al. 2009). Changes in the largest diameter (unidimensional measurement) of the tumor lesions and the short axis measurements in the case of lymph nodes are used in the RECIST guideline.

11.1 Schedule of Evaluations

For the purposes of this study, patients should be reevaluated every 8 weeks for the first year and then every 12 weeks after Year 1.

11.2 Definitions of Measurable and Non-Measurable Disease

11.21 Measurable Disease

11.211 A non-nodal lesion is considered measurable if its longest diameter can be accurately measured as ≥ 1.0 cm with CT scan, CT component of a PET/CT, or MRI.

11.212 A malignant lymph node is considered measurable if its short axis is >1.5 cm when assessed by CT scan (CT scan slice thickness recommended to be no greater than 5 mm).

NOTE:

Tumor lesions in a previously irradiated area are considered measurable disease under the following conditions:

- If they have progressed at screening evaluation

11.22 Non-Measurable Disease

All other lesions (or sites of disease) are considered non-measurable disease, including pathological nodes (those with a short axis ≥ 1.0 to <1.5 cm). Bone lesions, leptomeningeal disease, ascites, pleural/ pericardial effusions, lymphangitis cutis/pulmonis, inflammatory breast disease, and abdominal masses (not followed by CT or MRI), are considered as non-measurable as well.

Note: 'Cystic lesions' thought to represent cystic metastases can be considered as measurable lesions, if they meet the definition of measurability described above.

However, if non-cystic lesions are present in the same patient, these are preferred for selection as target lesions. In addition, lymph nodes that have a short axis <1.0 cm are considered non-pathological (i.e., normal) and should not be recorded or followed.

11.3 Guidelines for Evaluation of Measurable Disease

11.3.1 Measurement Methods:

- All measurements should be recorded in metric notation (i.e., decimal fractions of centimeters) using a ruler or calipers.
- The same method of assessment and the same technique must be used to characterize each identified and reported lesion at baseline and during follow-up. For patients having only lesions measuring at least 1 cm to less than 2 cm must use CT imaging for both pre- and post-treatment tumor assessments.
- Imaging-based evaluation is preferred to evaluation by clinical examination when both methods have been used at the same evaluation to assess the antitumor effect of a treatment.

11.3.2 Acceptable Modalities for Measurable Disease:

- Conventional CT and MRI: This guideline has defined measurability of lesions on CT scan based on the assumption that CT slice thickness is 5 mm or less. If CT scans have slice thickness greater than 5 mm, the minimum size for a measurable lesion should be twice the slice thickness.
- As with CT, if an MRI is performed, the technical specifications of the scanning sequences used should be optimized for the evaluation of the type and site of disease. The lesions should be measured on the same pulse sequence. Ideally, the same type of scanner should be used and the image acquisition protocol should be followed as closely as possible to prior scans. Body scans should be performed with breath-hold scanning techniques, if possible.
- PET-CT: If the site can document that the CT performed as part of a PET-CT is of identical diagnostic quality to a diagnostic CT (with IV and oral contrast), then the CT portion of the PET-CT can be used for RECIST measurements and can be used interchangeably with conventional CT in accurately measuring cancer lesions over time.
- FDG-PET: FDG-PET scanning is allowed to complement CT scanning in assessment of progressive disease [PD] and particularly possible 'new' disease. A 'positive' FDG-PET scanned lesion is defined as one which is FDG avid with an update greater than twice that of the surrounding tissue on the attenuation corrected image; otherwise, an FDG-PET scanned lesion is considered 'negative.' New lesions on the basis of FDG-PET imaging can be identified according to the following algorithm:
 - a. Negative FDG-PET at baseline with a positive FDG-PET at follow-up is a sign of PD based on a new lesion.
 - b. No FDG-PET at baseline and a positive FDG-PET at follow-up:
 - i. If the positive FDG-PET at follow-up corresponds to a new site of disease confirmed by CT, this is PD.

- ii. If the positive FDG-PET at follow-up is not confirmed as a new site of disease on CT at the same evaluation, additional follow-up CT scans (i.e., additional follow-up scans at least 4 weeks later) are needed to determine if there is truly progression occurring at that site. In this situation, the date of PD will be the date of the initial abnormal PDG-PET scan.
- iii If the positive FDG-PET at follow-up corresponds to a pre-existing site of disease on CT that is not progressing on the basis of the anatomic images, it is not classified as PD.

11.33 Measurement at Follow-up Evaluation:

- A subsequent scan must be obtained 4 weeks following initial documentation of an objective status of either complete response (CR) or partial response (PR).
- In the case of stable disease (SD), follow-up measurements must have met the SD criteria at least once after study entry at a minimum interval of 8 weeks (see Section 11.44).
- The cytological confirmation of the neoplastic origin of any effusion that appears or worsens during treatment when the measurable tumor has met criteria for response or stable disease is mandatory to differentiate between response or stable disease (an effusion may be a side effect of the treatment) and progressive disease.
- Cytologic and histologic techniques can be used to differentiate between PR and CR in rare cases (e.g., residual lesions in tumor types such as germ cell tumors, where known residual benign tumors can remain.)

11.4 Measurement of Effect

11.41 Target Lesions & Target Lymph Nodes

- Measurable lesions (as defined in Section 11.21) up to a maximum of 5 lesions, representative of all involved organs, should be identified as “Target Lesions” and recorded and measured at baseline. These lesions can be non-nodal or nodal (as defined in 11.21), where no more than 2 lesions are from the same organ and no more than 2 malignant nodal lesions are selected.
Note: If fewer than 5 target lesions and target lymph nodes are identified (as there often will be), there is no reason to perform additional studies beyond those specified in the protocol to discover new lesions.
- Target lesions and target lymph nodes should be selected on the basis of their size, be representative of all involved sites of disease, but in addition should be those that lend themselves to reproducible repeated measurements. It may be the case that, on occasion, the largest lesion (or malignant lymph node) does not lend itself to reproducible measurements in which circumstance the next largest lesion (or malignant lymph node) which can be measured reproducibly should be selected.
- Baseline Sum of Dimensions (BSD): A sum of the longest diameter for all target lesions plus the sum of the short axis of all the target lymph nodes will be calculated and reported as the baseline sum of dimensions (BSD). The BSD will be used as reference to further characterize any objective tumor response in the measurable dimension of the disease.

- Post-Baseline Sum of the Dimensions (PBSD): A sum of the longest diameter for all target lesions plus the sum of the short axis of all the target lymph nodes will be calculated and reported as the post-baseline sum of dimensions (PBSD). If the radiologist is able to provide an actual measure for the target lesion (or target lymph node), that should be recorded, even if it is below 0.5 cm. If the target lesion (or target lymph node) is believed to be present and is faintly seen but too small to measure, a default value of 0.5 cm should be assigned. If it is the opinion of the radiologist that the target lesion or target lymph node has likely disappeared, the measurement should be recorded as 0 cm.
- The minimum sum of the dimensions (MSD) is the minimum of the BSD and the PBSD.

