11.43 Response Criteria

- 11.431 All target lesions and target lymph nodes followed by CT/MRI/PET-CT/ must be measured on re-evaluation at evaluation times specified in Section 11.1. Specifically, a change in objective status to either a PR or CR cannot be done without re-measuring target lesions and target lymph nodes.

Note: Non-target lesions and non-target lymph nodes should be evaluated at each assessment, especially in the case of first response or confirmation of response. In selected circumstances, certain non-target organs may be evaluated less frequently. For example, bone scans may need to be repeated only when complete response is identified in target disease or when progression in bone is suspected.

11.432 Evaluation of Target Lesions

- Complete Response (CR): All of the following must be true:
 - a. Disappearance of all target lesions.
 - b. Each target lymph node must have reduction in short axis to <1.0 cm.
 - c. Normalization of tumor biomarkers.
- Partial Response (PR): At least a 30% decrease in PBSD (sum of the longest diameter for all target lesions plus the sum of the short axis of all the target lymph nodes at current evaluation) taking as reference the BSD (see Section 11.41).
- Progression (PD): At least one of the following must be true:
 - a. At least one new malignant lesion, which also includes any lymph node that was normal at baseline (<1.0 cm short axis) and increased to ≥ 1.0 cm short axis during follow-up.
 - b. At least a 20% increase in PBSD (sum of the longest diameter for all target lesions plus the sum of the short axis of all the target lymph nodes at current evaluation) taking as reference the MSD (Section 11.41). In addition, the PBSD

- must also demonstrate an absolute increase of at least 0.5 cm from the MSD.
- c. See Section 11.32 for details in regards to the requirements for PD via FDG-PET imaging.
 - Stable Disease (SD): Neither sufficient shrinkage to qualify for PR, nor sufficient increase to qualify for PD taking as reference the MSD.
- 11.433 Evaluation of Non-Target Lesions & Non-target Lymph Nodes
- Complete Response (CR): All of the following must be true:
 - a. Disappearance of all non-target lesions.
 - b. Each non-target lymph node must have a reduction in short axis to <1.0 cm.
 - c. Normalization of tumor biomarkers
 - Non-CR/Non-PD: Persistence of one or more non-target lesions or non-target lymph nodes and/or maintenance of tumor marker level above the normal limits.

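### Read literally, the progression reference (MSD) is the smaller of baseline and the current sum, so the size criterion for progression ignores regrowth from nadir

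*Combined protocol and SAP*

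**What the plan says.** Section 11.41 defines three sums. The BSD is the baseline sum. The second is a sum that "will be calculated and reported as the post-baseline sum of dimensions (PBSD"), with no evaluation named. The third is the progression reference: "The minimum sum of the dimensions (MSD) is the minimum of the BSD and the PBSD".

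Section 11.432 applies them. Partial response is a decrease of at least 30% from the BSD. Progression by target-lesion size begins "At least a 20% increase in PBSD (sum of the longest diameter for all target lesions" and continues "short axis of all the target lymph nodes at current evaluation) taking as reference the MSD (Section 11.41"). The sum "must also demonstrate an absolute increase of at least 0.5 cm from the MSD". Stable disease uses the MSD as well.

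Progression can also be declared by other routes:
- a new lesion (11.432 and 11.433);
- unequivocal non-target progression (11.433);
- FDG-PET findings (11.32);
- symptomatic deterioration (11.45).

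Duration of response (16.2221) and PFS (16.2223) both end at documented progression. The primary endpoint (16.11) is CR or PR on two consecutive evaluations at least 4 weeks apart.

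**The concern.** A progression rule for a trial with response as its primary endpoint needs a reference that falls as the tumour shrinks, so that regrowth after a response is recognised. Section 11.41 names only two quantities, the BSD and the PBSD, and the one gloss that ties the PBSD to a visit ties it to the current one. Nothing in Section 11 mentions a nadir, an earlier evaluation or the smallest sum to date.

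If the rule is applied as worded, the error falls on responders and grows with the depth of response. They are the whole denominator for duration of response and contribute to PFS. Progression status also decides who moves to event monitoring (13.1, 13.2), so the same wording determines on-study status.

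**Working it through.** **Inputs.** MSD = min(BSD, PBSD), from 11.41. PBSD = sum at the current evaluation, from the gloss in 11.432. PD by size requires PBSD ≥ 1.2 × MSD and PBSD − MSD ≥ 0.5 cm. PR requires PBSD ≤ 0.7 × BSD. The plan states no figure that rests on the MSD, so there is nothing to reproduce for this definition.

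**Step 1: literal rule.**
- If PBSD ≤ BSD, then MSD = PBSD. The increase is 0%, and PD by size is impossible.
- If PBSD > BSD, then MSD = BSD. PD needs PBSD ≥ 1.2 × BSD and at least 0.5 cm above BSD.

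The criterion therefore reduces to growth over baseline.

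**Step 2: thresholds with a baseline of 10.0 cm.** Nadir-based threshold = 1.2 × nadir. Literal threshold = 1.2 × 10.0 = 12.0 cm. Literal rise from nadir = 12.0/nadir − 1.

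| Nadir (cm) | PD, nadir reference (cm) | PD, literal (cm) | Rise from nadir needed, literal |
|---|---|---|---|
| 9.0 | 10.8 | 12.0 | 33% |
| 7.0 | 8.4 | 12.0 | 71% |
| 5.0 | 6.0 | 12.0 | 140% |
| 3.0 | 3.6 | 12.0 | 300% |

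For small sums the 0.5 cm floor governs the nadir-based rule. With baseline 3.0 cm and nadir 1.5 cm, 1.2 × 1.5 = 1.8 cm but the floor gives 2.0 cm. The literal threshold is 1.2 × 3.0 = 3.6 cm.

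**Step 3: delay in time (illustrative).** For baseline 10.0 cm and nadir 5.0 cm, the sum must go from 6.0 to 12.0 cm. Assume steady regrowth, 8-week scans and no other PD route firing first. At 20% per scan: ln 2/ln 1.2 = 3.8 intervals, about 30 weeks. At 10% per scan: ln 2/ln 1.1 = 7.3 intervals, about 58 weeks. The regrowth rates are assumptions, the calculation interpolates between scans, and 11.1 moves to 12-week scans after Year 1. If a new lesion appears first, the delay can be nil.

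**Step 4: confirmation of response.** A second sum can be PR against baseline and PD against nadir only if 1.2 × first sum ≤ 0.7 × BSD. That is, the first sum must be ≤ 0.7/1.2 = 58.3% of BSD, and the rise must also reach 0.5 cm. Example: 10.0 → 4.0 → 6.5 cm.
- Literal: MSD = min(10.0, 6.5) = 6.5, increase 0%. The sum is 35% below baseline, so PR is confirmed.
- Nadir reference: 6.5/4.0 = 1.625, up 62.5% and 2.5 cm. PD is met at the second scan, as is PR.

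Under the literal rule PR and PD by size cannot coincide (≤ 0.7 × BSD against ≥ 1.2 × BSD). Under a nadir reference they can, and 11.432 gives no order of precedence. The table in 11.441 takes target-lesion status as an input, so it does not settle this.

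**Step 5: Simon design (background check).** P(stop at stage 1) = (1 − p)^6. P(promising) is the exact binomial probability of at least 1 response in 6 and at least 4 in 23.

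| True rate | 10% | 15% | 20% | 25% | 30% |
|---|---|---|---|---|---|
| P(promising), recomputed | 0.149 | 0.368 | 0.585 | 0.748 | 0.852 |
| Stated in 16.13 | 0.15 | 0.37 | 0.59 | 0.75 | 0.85 |
| P(stop), recomputed | 0.531 | 0.377 | 0.262 | 0.178 | 0.118 |
| Stated in 16.13 | 0.53 | 0.38 | 0.26 | 0.18 | 0.12 |

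The stated table is reproduced to rounding and does not depend on the MSD.

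**The case against.** The strongest reply is that a running minimum was plainly intended. The definition in 11.41 does not itself contain the word current. That gloss sits in 11.432 and may only identify which of several accumulated sums is being compared with the reference. Calling the quantity a minimum sum, and keeping it apart from the BSD, has a purpose only if it can fall below baseline and stay there. Section 11.0 also commits the study to RECIST v1.1. An analyst might well program a running minimum without a second thought.

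This stands as evidence of intent, and it rules out one inference: a reader might conclude that the protocol deliberately adopts a baseline-only progression rule, and the text does not show that. But intent does not replace the definition. Section 11 writes out its own computing rules, and someone following them step by step obtains no nadir. Two tenable readings that give different progression dates are a defect in an endpoint definition.

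A reader might also infer that a responder cannot progress at all until 20% over baseline. That goes too far: the limit applies to the target-lesion sum only, and every other route listed above still leads to PD. The delays in weeks likewise cannot be taken as an expected effect, because no document gives regrowth rates in this disease.

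**Conclusion.** The point holds as a defect in the written definition. Read literally, 11.41 with 11.432 removes the nadir from the size criterion. With a 10.0 cm baseline, this puts PD at 12.0 cm instead of 8.4, 6.0 or 3.6 cm for nadirs of 7.0, 5.0 or 3.0 cm. If applied that way, duration of response and PFS are overstated in patients whose first sign of progression is target-lesion regrowth. How many such patients there would be cannot be derived from the documents, nor can the reading the analysts would program.

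A reader might infer that the primary analysis is compromised. It is not, in general: the Simon operating characteristics are unchanged, and confirmation is affected only when a first PR at or below 58.3% of baseline is followed by regrowth of at least 20% and 0.5 cm that still leaves the sum at or below 70% of baseline. That case should be rare. It is worth closing because the decision rules in 16.121 and 16.122 turn on a single response (0 versus 1 of 6, 3 versus 4 of 23). The correction should be made, since it is cheap and removes any doubt about two secondary endpoints.

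**What to change.** In 11.41, define MSD as the smallest sum of dimensions recorded at baseline or at any evaluation before the current one. Including the current evaluation would give the same PD calls, since a new minimum cannot be PD by size.

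In 11.432, add that an evaluation meeting both PR (against BSD) and PD (against MSD) is classified as PD. This sentence becomes necessary once the reference is the nadir.

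The cost is two sentences and a matching check in the response derivation. No new data, scans or patients are needed. Duration of response and PFS may be shorter than under the literal rule. If a running minimum is already programmed, the PD dates will not move. Because PD status also feeds Section 13, the sponsor should confirm that Sections 11 and 13 are applied with the same definition.
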